## 6.3 Site Suspension and Review

Study enrollment and initial islet transplants will be suspended (placed on hold) at a participating clinical site, pending expedited review of all pertinent data by the institutional review board (IRB), the NIAID, the NIDDK, and the NIDDK DSMB, if any one of the following occurs:

- 1. Any possibly study-related grade 5 adverse event; or
- 2. Two serious adverse events related to the islet infusion procedure (e.g. bleeding, thrombosis, gall bladder injury); or
- 3. Two consecutive primary non-functioning transplants defined as graft failure that occurs between 3-7 days post-transplant.

After any site is placed on hold, no additional transplants will be performed under this protocol at that site until the CIT Steering Committee and DSMB meet either in person or by conference call to review in depth the results and circumstances surrounding the islet functional failure or SAE to determine whether the trial enrollment of new subjects and conduct of additional transplants could be safely resumed at that site, or whether there could be implications for the continuation of the entire proposed protocol also at other affiliated sites.

In all cases of PNF, subjects will be asked to temporarily continue immunosuppression to decrease the risk of sensitization that could increase the risk of poor outcome should future transplants occur. A tapering schedule will be applied until immunosuppressants are completely discontinued.

#### 7. STUDY PROCEDURES 7.1 Enrollment and Screening

The site investigator or designated study personnel will explain the research study in lay terms and discuss available modes of treatment individually with every potential study patient referred to the Nordic Network for Clinical Islet Transplantation. If the patient is willing to participate and once the written consent is obtained, the subject is enrolled and the screening period begins. Patients who have been previously assessed for standard islet and/or pancreas transplantation at the participating sites may ultimately be enrolled in this trial and, as a result, may have some testing done prior to signing the consent document.

Enrollment into the study is done using an electronic internet entry system that can be accessed using any computer connected to the Internet. Authorized personnel will be required to log into the system using their assigned user identification and password. Allocation to a unique subject identification number is computer generated and assigned at the time of enrollment.

Subject eligibility will be confirmed through the performance of the screening visit procedures detailed in the Schedule of Events (Appendix 1). More than one visit may be necessary to complete all of the screening procedures. Results from assessments completed prior to signing informed consent, must be current within the windows stated in the table below.

Screening Assessments	Allowable timeframe prior to the date of consent
EBV IgG	No limit. Positive test result required for eligibility.
Retinopathy evaluation; Physical exam; Chest x-ray; Abdominal Ultrasound; ECG; Myocardial Scintigram; Conduction Velocity and RR intervals; Serology (HIV, Hepatitis B, Hepatitis C); CMV IgG and IgM; Coagulation Status (APTT, PK, fibrinogen, platelets)	Within one year
CBC w/ differential; Serum Chemistry Panel and CRP; Urine Albumin; Fasting Lipid Profile (Total, LDL, HDL, Triglycerides); GFR	Within 6 months
Quality of Life Questionnaires; Medial and Diabetes History Assessment; Panel Reactive Antibody (Alloantibodies); Record recipient HLA and Blood Type; Pregnancy Test; HBA1c; MMTT; FSIGT; LI; HYPO; Clarke Score; c-peptide to Glucose Creatinine ratio; Serum to Archive; PBMC and Plasma to Archive; RNA to Archive.	After informed consent has been obtained

#### Table 2.Screening Assessments Windows

The screening period ends when all information/results needed for evaluation of inclusion and exclusion criteria are available. If the screening is a success the subject should be placed on the waiting list for transplantation. A general waiting list for all subjects entering the study will be kept at the Rudbeck Laboratory in Uppsala, Sweden.

If there is a screening failure the subject should be documented as screening failure on the study screening log, and the subject is terminated from the study.

## 7.2 Waiting List / Baseline Visit

During the period when the subject is awaiting for their first transplant, they will return to the study site for clinic visits every 6 months. Waitlist assessments will be repeated at pre-defined intervals as detailed below. Results from assessments done closest to the date of randomization will be used as the subject's baseline values.

Waitlist Assessments	Timetable for repeat testing while on the waiting list
Retinopathy Evaluation; Physical Exam; Chest x-ray; ECG; Coagulation Status (APTT, PK, fibrinogen, platelets); CGMS; Serology (HIV, Hepatitis B, Hepatitis C	Once a Year
CBC with differential; Serum Chemistry Panel; Glycemic Lability- LI ( repeat only if used as inclusion criteria); Glycemic Lability (MAGE); Alloantibodies; Quality of Life Questionnaires (SF36, DTSQ); HbA1C; Blood Sugar Records and Hypo sheets; Full Hypo Score; Clarke Score.	Once every 6 months
Baseline Assessments	
Re-evaluation of the eligibility criteria; Record concomitant medications; CMV and EBV by PCR; Autoantibodies; RNA and Plasma to Archive; Alloantibodies; Physical Exam; CBC with differential; Serum Chemistry Panel; Coagulation Status (APTT, PK, fibrinogen, platelets); Blood Sugar Records and/or Hypo sheets; Serology (HIV, Hepatitis B, Hepatitis C); Chest x-ray; ECG; Cross Match; Serum Pregnancy Test; HbA1C	At the time the pancreas becomes available, prior to transplant

Table 3. Baseline/Waiting List Assessment Windows

## 7.3 Randomization and Study Treatment Schedule

Once a compatible islet prep becomes available, then the site personnel will re-confirm the eligibility criteria. Eligible subjects will be randomized (1:1), to the experimental arm or control arm. A total of 36 subjects will be randomized; 18 subjects to an experimental arm and 18 subjects to a control arm.

#### 7.3.1 Experimental Arm ("LMW-DS" Study Arm)

Eligible type I diabetic (T1D) subjects randomized to the "LMW-DS" arm will receive islets fulfilling release criteria from the islet isolation lab. Randomized subjects will receive protocol immunosuppression and LMW-DS, excluding heparin treatment, and in addition receive 1) and 2) below:

1. A bolus dose of 1.5 mg LMW-DS/kg BW given intravenous, another 3.0 mg LMW-DS/kg BW distributed in the islet bags given intraportally, and

2. Continuous intravenous infusion of LMW-DS started immediately after islet infusion and maintained for 5 hours, carefully adjusted to target an APTT of 150+10s according to Instructions for Administration of LMW-DS to Target APTT of 150+/- 10s Worksheet (available in the Manual of Procedures, as well as on the CIT Website).

#### 7.3.2 Control Arm ("State of the Art")

Eligible Type I diabetic subjects randomized to the "State of the Art" arm will receive islets fulfilling release criteria from the islet isolation lab. In addition, randomized subjects will receive protocol immunosuppression without LMW-DS, including anticoagulative treatment with heparin. A dose of 70 U/kg body weight of recipient with the islet infusion, followed by a continuous intraportal infusion of heparin targeting an APTT of 50+10s for the next 5 hours will be administered.

## 7.4 Transplantation

At least 5000 IEQ/kg shall be given at the first transplantation, and 4000 IEQ/kg for the second or third transplant.

### 7.4.1 First Islet transplantation (1)

The primary endpoint is determined based on the first islet transplantation. If necessary, a second islet transplant may occur at least 75 days after the first transplantation, and a third islet transplant may occur at least 28 days after the second islet transplant. All subsequent transplants must take place prior to 8 months after the first islet transplant.

Islets are suspended in medium and injected through a catheter placed in the portal vein, either through transhepatic cannulation or through a minimal surgical incision.

#### 7.4.2 Criteria and Timing for Subsequent Islet Transplant

If repeated transplantation (s) are needed the subject will follow the same protocol and will remain in the randomized study group previously assigned. Subjects who do not meet criteria for a subsequent transplant will enter the reduced follow-up schedule (Appendix 2).

**Partial Graft Function:** Islet transplant recipients who do not meet criteria for full islet graft function, but have either a basal or stimulated c-peptide level  $\geq 0.1$  nmol/L ( $\geq 0.3$ ng.mL), will be considered partial islet graft function.

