### At 365 ± 14 days following the first and final islet infusion:

- The proportion of subjects with full islet graft function
- The proportion of subjects with an HbA1c <7.0% and free of severe hypoglycemic events from day 28 through day 365
- The percent reduction in insulin requirements

- HbA1c
- MAGE
- LI
- Clarke score
- HYPO score
- Basal (fasting) and 90-min glucose and C-peptide (MMTT)
- β-score
- C-peptide:glucose creatinine ratio
- Acute insulin response to glucose (AIRglu), insulin sensitivity, and disposition index derived from the insulin-modified frequently-sampled intravenous glucose tolerance (FSIGT) test
- Glucose variability and hypoglycemia duration derived from the continuous glucose monitoring system® (CGMS)
- The proportion of subjects receiving a second islet infusion
- The proportion of subjects receiving a third islet infusion

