## 5.15.3 Premature Discontinuation of Study Treatment

Study treatment may be prematurely discontinued for any subject for any of the following reasons:1.

The subject is unwilling or unable to comply with the protocol.2. The investigator believes that the study treatment is no longer in the best interest of the subject.3. Graft Failure: Islet allograft failure will be defined as absence of insulin production by transplanted islets, as evidenced by absence of c-peptide <0.1nmol/L (<0.3 ng/mL). This will be determined by (1) c-peptide <0.1nmol/L (<0.3 ng/mL) on random testing, followed by (2) c-peptide<0.1nmol/L (<0.3 ng/mL) at baseline, and at 60 and 90 minutes after MMTT. C-peptide levels obtained in the course of the MMTT levels will be run at the core laboratory in Seattle, WA. Subjects with graft failure do not need to complete the day 75 metabolic assessments.

4. A unexpected related serious adverse event. The agent(s) to which the event is attributed will be discontinued.

Subjects who prematurely discontinue study treatment will remain in the study until normal termination, for the purpose of monitoring safety and efficacy parameters and will enter the reduced

schedule outlined in Appendix 2. Data from these subjects will be used in the intent-to-treat analysis. 6. Criteria for Premature Termination of the Study

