The option of a third islet infusion under this protocol will be considered if the subject is  $\geq$ 28 days (+/-3 days) following the second islet infusion, and if all of the following conditions are met:

- 1. The subject remains without full islet graft function;
- 2. There is evidence of partial graft function (C-peptide > 0.1nmol/L (>0.3ng/mL);
- 3. No evidence of post-transplant lymphoproliferative disorder (PTLD);
- 4. The CIT Principal Investigator and Site Principal Investigators have determined that there were no relevant protocol deviations at the site;
- 5. The subject has been compliant with study monitoring and prescribed immunosuppressive therapy;
- 6. No evidence of a serious and life-threatening infection, adverse event, or other condition that precludes attempting an intraportal injection or continuation of the post-transplant treatment regimen;
- No evidence of progressive renal dysfunction, with blood creatinine rising above 2.0 mg/dL (177 μmol/L);
- 8. No evidence of hypersensitization, allergic responses, or other potentially serious drug reactions to medications required by the protocol;
- 9. No evidence of abnormal liver ultrasound and LFTs within 1.5 times the upper limit of the normal range prior to the third transplant.
- 10. Less than 8 months has passed after the first islet transplantation.

Participants who have completed 8 months follow up post first infusion will no longer be eligible for additional islet infusions funded under this protocol.

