#### **10.2.2 SECONDARY ENDPOINTS**

The secondary endpoints are defined in section 3.1.2.

HbA1c levels will be categorized for example, as either normal (<= 7.0 %), or non-normal (>7.0%). Dichotomous variables such as HbA1c (normal/non-normal) and rate of severe hypoglycemic events will be analyzed using logistic regression analysis with a term for treatment. Should a dichotomous endpoint not be evaluated for a particular individual then a failure will be imputed unless an evaluation is done at a time longer than 75 days after transplant and before an additional islet cell infusion, in which case that later value will be imputed.

Continuous variables such as QOL scales will be analyzed by a t-test. If there is compelling evidence that the normal distribution does not hold then a logarithmic or square root transformation will be done before using the t-test. If lack of normality persists, non-parametric tests will be used.

By examining multiple secondary endpoints it is likely that some variables will be found significantly different between the two treatment groups, but these findings may be Type I errors. Appropriate qualifiers will be reported with any significant secondary findings.

Regression models for longitudinal data (mixed models) will be used to examine the differences between groups in each of the response variables (HbA1c level and C-peptide levels) where measurements are repeated over time. Mixed models for dichotomous variables will be used to model full islet graft function over time. Survival analysis models will be used to compare time to becoming insulin dependent and to identify risk factors through Kaplan-Meier estimates and Cox regression models.

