## APPENDIX 2. REDUCED FOLLOW-UP SCHEDULE

Subjects withdrawn from study therapy should be followed according to the reduced follow-up schedule provided below. All reduced follow-up assessments should be scheduled relative to the day on which the study treatment is discontinued. The last follow-up visit will vary depending on when the subject discontinues study therapy and should be done at 1-year post the subject's **last** transplant.

Complete the following assessments at the intervals (+/- 7 days) indicated below relative to the day the subject discontinued study treatment. Continue conducting these assessments at the defined intervals until the subject reaches one year post **last** transplant.

- Assess SAEs and hypoglycemic events: q1 month. If subject does not come to the study site for the visit, attempt to obtain information via a phone contact.
- Alloantibody (central lab): q 1 month for the first 3 months and q 3 months thereafter.

Complete the following assessments at 1-year (+/- 14 days) post initial transplant:

- Assess SAEs and hypoglycemic events
- Alloantibody (central lab)
- HbA1c (central lab)
- 90 minute c-peptide post MMTT (central lab)
- Serum creatinine (central lab)
- QOL questionnaire (via mail or in-person)

Complete the following assessments at 1-year (+/- 7 days) post **last** transplant:

- Assess SAEs and hypoglycemic events
- QOL questionnaire (via mail or in-person)

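### Section 7.4.2 sends every subject who does not qualify for another infusion to the reduced schedule, contradicting Appendix 2, 5.15.3 and 7.5; if followed, day-365 full graft function could not be classified

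*Protocol*

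**What the plan says.** Section 7.4.2, on subsequent transplants, states: "Subjects who do not meet criteria for a subsequent transplant will enter the reduced follow-up schedule (Appendix 2". No group is exempted.

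Appendix 2 describes its own population differently: "Subjects withdrawn from study therapy should be followed according to the reduced follow-up schedule provided below". Its clock is also specific: "All reduced follow-up assessments should be scheduled relative to the day on which the study treatment is discontinued". Section 5.15.3 uses the same trigger. It says "Subjects who prematurely discontinue study treatment will remain in the study until normal termination, for the purpose of monitoring safety and efficacy parameters", and sends those subjects to Appendix 2.

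Section 7.5 schedules clinical evaluations at months 6 and 12 for subjects in general. Section 7.6 expects insulin-free subjects to go on recording glucose up to 12 months. Appendix 1 has month-12 and one-year-after-first-transplant columns, and its footnote 10 requires GFR one year after the first and final transplants.

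Section 4.1.3 lists, at day 365 after the first and final infusion, "The proportion of subjects with full islet graft function". For missing dichotomous endpoints, section 10.2.2 says: "Should a dichotomous endpoint not be evaluated for a particular individual then a failure will be imputed". The exception is an evaluation made more than 75 days after transplant and before a further infusion.

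**The concern.** A subject with full graft function does not meet the criteria for another infusion. Taken as written, 7.4.2 therefore moves the trial's successes, still on study treatment, to a schedule built for subjects who have stopped. It also moves partial-function subjects who are barred from re-infusion.

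At stake are the day-365 secondary efficacy and safety endpoints. Whether they were measured would depend on how the graft was doing, and the one dichotomous endpoint that expresses graft success would be scored as failure because it was not measured. Sites could reasonably follow either instruction, so the loss could also differ between centers.

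**Working it through.** **1. Who the sentence covers.** Among the third-infusion conditions is: "The subject remains without full islet graft function". A full-function subject fails that condition. Time also excludes everyone: "Participants who have completed 8 months follow up post first infusion will no longer be eligible for additional islet infusions funded under this protocol". Read literally, the rule would therefore move every subject off Appendix 1 between month 8 and month 12 after the first infusion.

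**2. The passages side by side.**

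| Place | Who is on the reduced schedule | Timing |
|---|---|---|
| 7.4.2 | anyone not meeting criteria for another infusion | none stated |
| Appendix 2 | subjects withdrawn from study therapy | from the day of discontinuation |
| 5.15.3 | subjects who stop study treatment early | refers to Appendix 2 |
| 7.5, 7.6, Appendix 1 | full follow-up expected, including insulin-free subjects | through month 12 |

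A subject still on treatment has no discontinuation day, so Appendix 2 cannot be timed for that subject. The first row cannot be reconciled with the other three.

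**3. What Appendix 2 would leave at day 365.** At one year after the initial transplant it lists SAEs and hypoglycemic events, alloantibody, HbA1c, 90-minute MMTT C-peptide, creatinine and quality of life. At one year after the last transplant it lists only SAEs, hypoglycemic events and quality of life.

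- Still evaluable one year after the first infusion: HbA1c, the composite of HbA1c below 7.0% with no severe hypoglycemia, and 90-minute C-peptide.
- Not evaluable: full graft function. All three statements of the definition (Study Definitions Page, synopsis, 4.1.3.1) require a central-laboratory fasting serum glucose. The first two also require a 90-minute MMTT glucose. Appendix 2 lists neither.
- Also not collected: insulin requirement at a study visit, MAGE, LI, Clarke, HYPO, fasting glucose and C-peptide (so no β-score or CPGCR), FSIGT, CGMS, measured GFR and the retinopathy assessment.

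**4. Imputation.** Full graft function is dichotomous and unevaluated, so 10.2.2 gives failure. Once a subject is on Appendix 2, no later evaluation of it is scheduled that could trigger the exception. Continuous measures would simply be missing.

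**5. Size.** The protocol gives no expected day-365 function rate, so there is no figure of its own to reproduce on this point. Its power statement concerns day-75 C-peptide and is not affected: noncentrality 1.0 / (0.9 × √(2/18)) = 3.33 on 34 df gives 89.9%, agreeing with the stated 90%.

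For illustration, let p be the true rate of full function and f the fraction of responders moved to Appendix 2, the same in both arms. The observed rate is p(1 − f), the observed difference is (p₁ − p₂)(1 − f), and the expected successes lost per arm are 18·f·p. Power is for an exact two-sided 5% Fisher test with 18 per arm, used here for convenience (10.2.2 plans logistic regression). All rates are assumptions.

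| True rates (LMW-DS vs control) | f = 0 | f = 0.5 | f = 1 |
|---|---|---|---|
| 50% vs 20% | 36% power | 25% vs 10%, 12% power | 0 vs 0 |
| 60% vs 30% | 36% power | 30% vs 15%, 10% power | 0 vs 0 |
| 70% vs 30% | 61% power | 35% vs 15%, 17% power | 0 vs 0 |

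In the middle row the expected successes lost are 18 × 0.5 × 0.6 = 5.4 vs 18 × 0.5 × 0.3 = 2.7 at f = 0.5, and 10.8 vs 5.4 at f = 1. A consistent literal reading is f = 1; intermediate values stand for sites that differ in how they read the sentence.

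**The case against.** The best defense is context. The sentence before the disputed one in 7.4.2 speaks of subjects who need a repeat transplant, and an insulin-free responder does not. Sections 7.5 and 7.6 and Appendix 1 plainly expect such subjects to be followed to month 12. The literal reading would also empty the month-12 and one-year columns, which nobody can have intended. This is a good argument about intent, and it shows that the text is a contradiction, not a settled instruction to drop responders. It does not remove the conflict. Even on that narrow reading, partial-function subjects on treatment who need another infusion but are barred from it go to Appendix 2 and lose most day-365 assessments.

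Other parts of the defense stand:

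- Section 8.2.1 requires all AEs to be collected until study completion, and 7.6 requires self-recorded glucose and insulin. Those data are not counted as lost here, although Appendix 2 has no diary-collection visit.
- A site running the whole MMTT of 9.1.1.5 would draw glucose as well, but Appendix 2 asks only for the 90-minute C-peptide.
- The exception in 10.2.2 is worded around day 75. Applying the rule to day 365 is the natural reading, but it is not spelled out.

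Two stronger inferences are tempting and not supported. A reader might conclude that day-365 efficacy could not be measured at all; step 3 shows that three efficacy measures survive after the first infusion. A reader might also conclude that the treatment difference could change sign, with single-infusion responders lost and second-infusion responders kept. Second-infusion responders equally fail the third-infusion criteria, so the rule, applied consistently, removes them too. A reversal would need a larger fraction moved in the LMW-DS arm (with 60% vs 30% and none moved in the control arm, more than half), and nothing in the protocol implies that.

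**Conclusion.** The contradiction is real and sits in an operative follow-up rule. If 7.4.2 is followed, day-365 full graft function cannot be classified and is scored as failure. The difference between arms then shrinks by the factor (1 − f), to zero when the rule is applied to everyone. Most other day-365 metabolic measures, GFR and retinopathy would be missing according to outcome.

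The severity is moderate. Only secondary endpoints are touched, and a responder's day-75 primary endpoint is unaffected because eligibility for another infusion is normally settled at or after that visit. The size rests on assumed response rates and an equal fraction moved in each arm. The contradiction itself rests on no assumption.

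**What to change.** Reconcile 7.4.2 with 5.15.3, 7.5 and Appendix 2. In 7.4.2, limit the reduced schedule to subjects who have discontinued study treatment. State that all other subjects, whether or not eligible for another infusion, stay on Appendix 1 through day 365 after the first and final infusion.

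The cost is one reworded sentence and a notice to sites. No visit or test is added, because Appendix 1 already schedules them. Once 7.4.2 is limited in this way, Appendix 2 needs no new items to resolve this point. Assessments missed at day 365 cannot be recovered later, so the change should be made before subjects reach the 8-month limit.
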